Ad hoc Clinic Visits: Only subjects with RVNA concentrations <0.5 IU/mL at the first visit of this extension study (Day 1, Year 3) or at the following yearly Scheduled Clinic Visits (from Year 4 to Year 9) will receive a booster vaccination (a single dose of 1.0 mL to be administered intramuscularly preferably in the deltoid region of the non-dominant arm) with GSK PCEC rabies vaccine. The booster dose will be given in an “Ad hoc Clinic Visit” which is planned to occur as soon as the results of the antibody assay will be available and within approximately 6 to 9 months from the blood draw taken during a previous “Scheduled Clinic Visit”. Prior to receipt of booster vaccination, subjects must be evaluated to confirm that they are eligible for vaccination.		
Subjects who will receive a booster vaccination will be observed at the site for at least 30 minutes after vaccination for any immediate reactions and will continue yearly procedures up to Year 10.		
For subjects receiving PCEC rabies booster vaccination, SAEs and the associated concomitant medications will be collected starting from the booster administration and until the day of next Scheduled Clinic Visit.		
Additional Clinic Visit: To investigate the prompt boostability of the immune response, additional blood samples will be drawn approximately 7 days after the Ad hoc Clinic Visits, only for subjects who will receive booster dose of PCEC rabies vaccine.		
If, after having received a booster dose, the subject does not reach the adequate antibody concentration (i.e., RVNA \geq 0.5 IU/mL) at two consecutive determinations, neither at 7 days after the booster dose (i.e. Additional Clinic Visit) nor at the next yearly evaluation (i.e., Scheduled Clinic Visit), an additional booster dose may be administered at the following Ad hoc Clinic Visit. If the subject is still non-responder, subsequent management should be at the discretion of the investigator.		
Should a subject have RVNA concentrations below 0.5 IU/mL at blood draw performed at the final Scheduled Clinic Visit (Year 10), the investigator will invite the subject to receive a booster dose of the rabies vaccine outside the study following standard clinical practice and there will be no further analyses performed on this additional vaccination.		

Name of Sponsor: GlaxoSmithKline Biologicals S.A.	Protocol number: V49_23E1	Generic name of study vaccine(s): Rabies, whole virus vaccine (inactivated)

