
• Geometric Mean Antibody Concentrations (GMCs) at Year 3, 4, 5, 6, 7, 8, 9 and 10;• Reverse Cumulative Distribution Plots (RCDPs) at Year 3, 4, 5, 6, 7, 8, 9 and 10;• Percentages of subjects with RVNA concentrations ≥ 0.5 IU/mL, as measured by RFFIT assay at Year 3, 4, 5, 6, 7, 8, 9 and 10.		

Name of Sponsor: GlaxoSmithKline Biologicals S.A.	Protocol number: V49_23E1	Generic name of study vaccine(s): Rabies, whole virus vaccine (inactivated)
Statistical Analyses:		
Time to first RVNA concentrations <0.5 IU/mL		
Kaplan-Meier estimate of the survival function, along with 95% CIs, will be computed and displayed per each vaccination regimen. The Cox regression model will be used to compare the 3 vaccine regimens every year.		
Geometric Mean Concentration (GMC) and Geometric Mean Ratio (GMR)		
RVNA GMCs will be based on the logarithmically transformed (base10) values.		
GMCs, with the associated 95% confidence intervals will be computed for each vaccine group (assigned from parent study) at Year 3, 4, 5, 6, 7, 8, 9 and 10 by taking the exponential of the corresponding log-transformed (least squares) means and 95% confidence intervals, from an ANOVA model with fixed factors for group and center. Group differences along with 95% CIs will also be computed. Subjects will be included in this analysis until they receive the booster dose and they will be excluded thereafter.		
For subjects receiving a booster dose, analysis of boostability will be conducted 7 days (and also approximately 6 to 9 months) after administration of the booster dose by providing GMRs and associated 95% CIs, considering the antibody value at the booster visit as baseline (denominator) and the antibody concentration at 7 days (and also approximately between 6 to 9 months) after booster as the numerator.		
Reverse Cumulative Distribution Plots at Year 3, 4, 5, 6, 7, 8, 9 and 10;		
Reverse cumulative distribution plots will be provided at Year 3, 4, 5, 6, 7, 8, 9 and 10 by vaccination regimen group.		
Percentages of subjects with RVNA concentrations ≥0.5 IU/mL		
As a form of supplementary information, also percentage of subjects with RVNA concentrations ≥ 0.5 IU/mL, as measured by RFFIT assay at Year 3, 4, 5, 6, 7, 8, 9 and 10 will be presented in a tabular fashion.		
Interim Analyses: In order to understand complete evolution of the antibody decay over time and the effect		

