^b SAEs and the associated concomitant medications will be collected ONLY from those subjects who will receive booster vaccine during *the Ad hoc Clinic Visit, starting from the time of booster administration until completion of safety follow-up period (the day of the next Scheduled Clinic Visit after booster vaccination or on the date of Early Termination Visit, whichever is earlier)*.

^c Subjects who terminate the study early are recommended to complete certain study-related procedures. See [section 5.5](#) for further details.

^d *Physical exams have to be done by practitioners in accordance with their institutional policy. Should the physical assessment reveal any abnormal values or events, which fall under definition of SAE, these must be documented in the CRF Adverse Events Form and reported to sponsor.*

**Visit 1 date to be used as reference for calculating next visit date (e.g. V1: 31 JAN 15, V2: 31 JAN 16 ± 28 days, V3: 31 JAN 17 ± 28 days).*

Table 2b Ad hoc and Additional Clinic Visit (Amended 25 February 2019)

Visit Type		Clinic Visit													
		Ad hoc ^a	Additional ^b	Ad hoc ^a	Additional ^b	Ad hoc ^a	Additional ^b	Ad hoc ^a	Additional ^b	Ad hoc ^a	Additional ^b	Ad hoc ^a	Additional ^b	Ad hoc ^a	Additional ^b
Study Period	Year 3, between 6 to 9 months after Schedule d Clinic Visit 1	Year 3, 7 days after Ad hoc Clinic Visit 1.1	Year 4, between 6 to 9 months after Schedule d Clinic Visit 2	Year 4, 7 days after Ad hoc Clinic Visit 2.1	Year 5, between 6 to 9 months after Schedule d Clinic Visit 3	Year 5, 7 days after Ad hoc Clinic Visit 3.1	Year 6, between 6 to 9 months after Schedule d Clinic Visit 4	Year 6, 7 days after Ad hoc Clinic Visit 4.1	Year 7, between 6 to 9 months after Schedule d Clinic Visit 5	Year 7, 7 days after Ad hoc Clinic Visit 5.1	Year 8, between 6 to 9 months after Schedule d Clinic Visit 6	Year 8, 7 days after Ad hoc Clinic Visit 6.1	Year 9, between 6 to 9 months after Schedule d Clinic Visit 7	Year 9, 7 days after Ad hoc Clinic Visit 7.1	
Visit Window (Days)	n/a	-1 to +1	n/a	-1 to +1	n/a	-1 to +1	n/a	-1 to +1	n/a	-1 to +1	n/a	-1 to +1	n/a	-1 to +1	
Visit Number	1.1	1.2	2.1	2.2	3.1	3.2	4.1	4.2	5.1	5.2	6.1	6.2	7.1	7.2	
Study Event	References														
Medical History ^c	Section 5.1.2	X		X		X		X		X		X		X	
Physical Exam ^c	Sections 5.1.2 and 5.2	X		X		X		X		X		X		X	
Pregnancy Test ^{c, d}	Sections 3.5 and 5.1.2	X		X		X		X		X		X		X	

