8.4.2.3.3 Statistical Methods (Amended 25 February 2019)

Time to first RVNA concentrations <0.5 IU/mL.

For each subject time to first RVNA concentrations <0.5 IU/mL will be calculated. Kaplan-Meier (**KM**) estimate of the survival function, along with 95% CIs, will be estimated and displayed per each vaccination regimen. Standard errors of the KM estimates will be based on the Greenwood's method; 25th and 75th percentile and median survival will be provided if estimable.

In this setting, the event/failure will be represented by the administration of the booster dose. Subjects without event will be regarded as right-censored data. Dropouts will be considered as non-informative data and judged as Missing Completely At Random (MCAR) as an association between the missingness mechanism and the vaccine efficacy or safety is implausible.

Group comparisons for first occurrences of a boost will be performed using the unadjusted Cox proportional hazard regression model (only treatment effect will be included). Ties will be handled with the exact method as it assumes that there is a true but unknown ordering for the tied event times. Hazard **Ratios** (HR) and 95% CIs will be computed. In case of not estimable HRs, alternative methods will be attempted.

It is expected that no or very few subjects will need more than one booster dose during the study conduct. Nevertheless, a contingency analysis will be performed counting the frequency of subjects who receive 0 booster, 1 booster, 2 boosters, 3 or more boosters.

If a relevant number of subjects will need more than one booster dose during the study conduct, the Andersen-Gill method will be used to analyze multiple events data.

Geometric Mean Ratio (GMR).

RVNA GMCs will be based on the logarithmically transformed (base10) values.

For subjects receiving a booster dose, analysis of boostability will be conducted 7 days and at also approximately 6 months after administration of the booster dose by providing GMRs and associated 95% CIs, considering the antibody value at the booster visit as baseline (denominator) and the antibody concentration at 7 days (and approximately at 6 months) after booster as the numerator.

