*Visit 1 date to be used as reference for calculating next visit date (e.g. V1: 31 JAN 15, V2: 31 JAN 16 ± 28 days, V3: 31 JAN 17 ± 28 days). Additional 14 days will be added to the time window for the inclusion to the PPS (time window will be ± 42 days). It was deemed that additional 14 days would not impact the analysis of immunogenicity persistence.

Table 3 Times and Events Table(s) - Ad hoc and Additional Clinic Visit

Visit Type		Clinic Visit													
		Ad hoc ^a	Additional ^b	Ad hoc ^a	Additional ^b	Ad hoc ^a	Additional ^b								
Study Period	Year 3, between 6 to 9 months after Schedule d Clinic Visit 1	Year 3, 7 days after Ad hoc Clinic Visit 1.1	Year 4, between 6 to 9 months after Schedul ed Clinic Visit 2	Year 4, 7 days after Ad hoc Clinic Visit 2.1	Year 5, between 6 to 9 months after Schedul ed Clinic Visit 3	Year 5, 7 days after Ad hoc Clinic Visit 3.1	Year 6, between 6 to 9 months after Schedul ed Clinic Visit 4	Year 6, 7 days after Ad hoc Clinic Visit 4.1	Year 7, between 6 to 9 months after Schedul ed Clinic Visit 5	Year 7, 7 days after Ad hoc Clinic Visit 5.1	Year 8, between 6 to 9 months after Schedul ed Clinic Visit 6	Year 8, 7 days after Ad hoc Clinic Visit 6.1	Year 9, between 6 to 9 months after Ad hoc Clinic Visit 7.1	Year 9, 7 days after Ad hoc Clinic Visit 7.1	
	n/a	-1 to +1	n/a	-1 to +1											
Visit Window (Days) Visit Number	1.1	1.2	2.1	2.2	3.1	3.2	4.1	4.2	5.1	5.2	6.1	6.2	7.1	7.2	
	Study Event	Protocol references													
Medical History ^c	Section 5.1.2	X		X		X		X		X		X		X	
Physical Exam ^c	Sections 5.1.2 and 5.2	X		X		X		X		X		X		X	
Pregnancy Test ^{c,d}	Sections 3.5 and 5.1.2	X		X		X		X		X		X		X	
Verification of Relevant Exclusion/Inclusion Criteria ^c	Section 4.0	X		X		X		X		X		X		X	
Vaccination ^e	Section 5.2	X		X		X		X		X		X		X	
30 Minutes Post Booster Injection Assessment	Section 5.2.1	X		X		X		X		X		X		X	
Assess SAEs and Relevant Concomitant Medications ^f	Sections 7.1.4, 5.1.2 and 6.5	X	X	X	X	X	X	X	X	X	X	X	X	X	X
Immunogenicity															
Serology Blood Draw	Section 3.5		X		X		X		X		X		X		X
Observe for at Least 15 Minutes Post Blood Draw and Assess AEs (if any)	Section 7.1.3		X		X		X		X		X		X		X

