- ^a Ad hoc Clinic Visit (which is planned to occur as soon as the results of the antibody assay will be available and within approximately 6 months from the blood draw taken during a previous "Scheduled Clinic Visit") is only applicable for those subjects with RVNA concentrations <0.5 IU/mL during this extension study. See sections 3.1 and 3.9 of Protocol Amendment 2 for further details.
- ^b Additional Clinic Visit (within approximately 7 days from Ad hoc Clinic Visit) only applicable for subjects who will receive a booster dose of PCEC rabies vaccine during Ad hoc Clinic Visit.
- ^c Procedure to be performed prior to vaccination. Physical exams have to be done by practitioners in accordance with their institutional policy. Should the physical assessment reveal any abnormal values or events, which fall under definition of SAE, these must be documented in the CRF Adverse Events Form and reported to sponsor.
- ^d Only for female subject of childbearing potential who are eligible to receive the booster dose.
- ^e GSK Biologicals' Randomization System on Internet (SBIR) will be used for Treatment allocation.
- ^f SAEs and the associated concomitant medications will be collected starting from the booster administration and until the completion of safety follow-up period (the day of the next Scheduled Clinic Visit after booster vaccination or on the date of Early Termination Visit, whichever is earlier).

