7.7. Overview of Analysis Sets by PD Code

Table 4 Safety Sets: applicable to Exposed to Booster dose subjects only

PD code	PD Description and Exclusion Reasons	Study Objective/Period	Exposed Set	Safety Set	
			Exclusion code	EXPFL	SAFFL
1070	incomplete treatment course. Booster was not administered although subject had RVNA concentration of <0.5 IU/mL	All Study		EXC	EXC
2150	Subject did not provide any post-booster safety data	Approx. 6 months after booster exposure*			EXC

* For further details refer to study protocol

EXC = excluded from this analysis set.

Table 5 Immunogenicity Sets

PD code	PD Description and Exclusion Reasons	All ENROLLED	FAS 1	FAS 2	PPS 1	PPS 2
		Exclusion code	ENRFL	FAS10FL	FAS20FL	PPS10FL
800	Fraudulent data		EXC	EXC	EXC	EXC
900	Signed informed consent not available on site				EXC	EXC
900	Wrong informed consent version signed				EXC	EXC
900	Informed consent not signed and/or dated by subject				EXC	EXC
900	Informed consent not signed and/or dated by appropriate site staff.				EXC	EXC
900	Informed consent not signed prior to any study procedure (examples: a, b, c)				EXC	EXC
900	Other informed consent deviations				EXC	EXC
910	Partially or inappropriately signed ICF				EXC	EXC
1070	Booster was administered although subject had RVNA concentration ≥ 0.5 IU/mL			EXC	EXC	EXC
1070	Route of administration is wrong or unknown				EXC	
1070	Administration of booster vaccine at wrong visit				EXC	
1070	Commercial vaccine used in place of study vaccine (but same vaccine)				EXC	
1070	Study treatment administered while contraindication				EXC	
1070	Study treatment not prepared as per protocol (e.g. reconstitution)				EXC	
1070	Incorrect Volume was given				EXC	
1080	Use of study treatment impacted by a temperature excursion which was not reported or approved, or which was disapproved for further use.				EXC	
1090	Expired study treatment administered				EXC	
2010	Eligibility Criteria Not Met				EXC	EXC
2040	Prohibited concomitant medication (interval + type)				EXC	EXC
2040	Prohibited concomitant vaccination (interval + type)				EXC	EXC

PD code	PD Description and Exclusion Reasons	All ENROLLED	FAS 1	FAS 2	PPS 1	PPS 2
		ENRFL	FAS10FL	FAS20FL	PPS10FL	PPS20FL
2040	Other excluded medication, vaccine or device deviation				EXC	EXC
2090	Blood draw after booster dose outside 7 (+/- 1 day) day interval				EXC	EXC

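### Under the Table 2b booster timing, the later post-booster sample falls nominally 3 to 6 months after the booster, not at the stated 6 to 9 months or approximately 6 months

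*Protocol*

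**What the plan says.** **Label of the later sample.** In the Protocol Synopsis (Statistical Analyses), "analysis of boostability will be conducted 7 days (and also approximately 6 to 9 months) after administration of the booster dose". SAP 8.8 lists the same 6-to-9-month time point. Protocol 8.4.2.3.3 says "analysis of boostability will be conducted 7 days and at also approximately 6 months after administration of the booster dose". SAP 11.2 also uses 6 months and, for the percentage at or above 0.5 IU/mL, equates it with the subsequent annual visit. On the safety side, SAP 13.3 describes the next Scheduled Clinic Visit as about 6 months after the booster, and SAP Table 4 has "Approx. 6 months after booster exposure".

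**Timing of the annual visits.** They are yearly, with a window of ±28 days. The Table 2a footnote gives the anchor: "Visit 1 date to be used as reference for calculating next visit date". For the per-protocol set, the SAP Table 2 footnote widens this: "time window will be ± 42 days".

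**Timing of the booster.** The documents give three versions:
- The Table 2b column header, repeated in SAP Table 3, reads "between 6 to 9 months after Schedule d Clinic Visit 1", and likewise for later visits.
- The Synopsis text, Table 2b footnote a and Protocol 5.2 place it "as soon as the results of the antibody assay will be available and within approximately 6 to 9 months from the blood draw".
- SAP Table 3 footnote a has "within approximately 6 months from the blood draw taken during a previous" Scheduled Clinic Visit.

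**The concern.** The month labels describe the time since the booster, but they look like the time from the preceding annual visit to the booster. The two intervals sum to about 12 months, so both can be 6 months, but both cannot run from 6 to 9 months.

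The label is the reported time point for the later GMR, for the pooled ANOVA at that time point in Protocol 8.4.2.3.3, and for the percentage at or above 0.5 IU/mL. That percentage at subsequent Scheduled Clinic Visits is part of a primary endpoint listed in the Synopsis. A reader will take these results as evidence on how long the booster response lasts. If antibody declines after its post-booster peak, a sample drawn at 3 to 6 months but labelled 6 to 9 months makes the response look more durable than the data show. The Year 6 interim report might go to a health authority.

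**Working it through.** **Which sample supplies the later value.** Under Protocol 3.5 and 7.3, serology after a booster is drawn only at the 7-day Additional Clinic Visit and at the annual visits. No separate draw is planned at 6 or 9 months. The annual visit after next falls 24 − 9 = 15 to 24 − 6 = 18 months after the booster, so it cannot be the one meant. The later value is the next annual visit, as SAP 11.2 says.

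**Formula.** Gap from booster to next annual visit = 12 months − time from preceding annual visit to booster.

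**Can the stated labels be reproduced?**
- A gap of 6 to 9 months needs a booster 12 − 9 = 3 to 12 − 6 = 6 months after the annual visit. This meets Table 2b only at 6 months.
- A gap of 6 months needs every booster at exactly 6 months.

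**Nominal gap under Table 2b** (month = 30.4375 days, year = 365.25 days):
- Booster at 9 months: 365.25 − 9 × 30.4375 = 91.3 days (3 months).
- Booster at 6 months: 365.25 − 6 × 30.4375 = 182.6 days (6 months).

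**Effect of visit windows.** Visit 1 is the anchor, so after a Visit 1.1 booster only Visit 2 varies. After boosters 2.1 to 7.1, both the preceding and the following annual visit vary.

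| Booster | ±28 days | ±42 days (PPS) |
|---|---|---|
| 1.1 | 91.3 − 28 to 182.6 + 28 = 63 to 211 days | 91.3 − 42 to 182.6 + 42 = 49 to 225 days |
| 2.1 to 7.1 | 91.3 − 56 to 182.6 + 56 = 35 to 239 days | 91.3 − 84 to 182.6 + 84 = 7 to 267 days |

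The windows widen the range equally at both ends and do not move its centre.

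**Share of samples at 6 months or later.** This needs an assumption that the documents do not give: booster timing uniform over 6 to 9 months (a span of 91.3 days) and each visit uniform within ±28 days. The share is the expected positive part of the window shift divided by 91.3.
- Booster 1.1: (28/4)/91.3 = 7/91.3 = 7.7%.
- Later boosters, where the shift is the difference of two uniform variables: (56/6)/91.3 = 9.33/91.3 = 10.2%.

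On the same assumption the mean gap is (3 + 6)/2 = 4.5 months, and 33% to 34% of samples fall before 4 months.

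**Range over that assumption.** All boosters at 6 months give a nominal gap of 6.0 months; all at 9 months give 3.0 months. A booster at 3 months, which the looser Synopsis wording and the SAP footnote do not exclude, would give 9 months.

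**The case against.** The strongest reply is that Table 2b's header is only one reading. Its own footnote a, the Synopsis and Protocol 5.2 call for the booster once assay results are available, with no clear lower bound, and the SAP footnote says within about 6 months. A booster at 3 to 6 months would make the 6-to-9-month label exactly right. SAP 11.2 also describes the baseline sample as taken about six months before the booster, and 6 + 6 = 12 makes its 6-month label coherent. On this view the firm defect is inconsistent booster timing, and the mislabelling is conditional.

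The conditionality stands, and the finding is limited to Table 2b timing. It is not a marginal reading, however. The Amendment 2 rationale records that the team agreed on 6 to 9 months after the Scheduled Clinic Visit, and the SAP Table 3 header repeats it. The SAP's 6-month account contradicts that header, and no single month label fits all the passages.

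Other points stand in part:
- No sample, model or analysis set changes. The Synopsis defines the percentage endpoint by visit, and no hypothesis is tested. The problem is the reported time point.
- Uniform timing is an assumption, and it fits poorly with giving the booster as soon as results arrive.
- The ±42-day limits apply only to the PPS, which is analysed only if it differs from the FAS by more than 10% (SAP 7.4). They also need coincident extremes.
- Amendment 2 dates from February 2019, with the study already running, so Table 2b may not describe earlier boosters.
- SAE collection is defined by visit and is unaffected. Only the month gloss in SAP 13.3 and Table 4 is inaccurate.

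**Conclusion.** The concern holds. With boosters timed as in Table 2b, the sample labelled 6 to 9 months is nominally taken 3 to 6 months (91 to 183 days) after the booster, and the approximately-6-months label is the upper end of that range rather than its typical value. This rests only on yearly visits, the Table 2b header, and SAP 11.2's use of the next annual visit. The 4.5-month mean and the 8% to 10% at 6 months or later rest additionally on uniform timing. Booster timing actually achieved could move the gap in either direction. The listed day-7 GMR endpoint is unaffected. This should be fixed before the final report, because it changes what the later results can be said to show about booster durability.

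**What to change.** - In the Protocol Synopsis, Protocol 8.4.2.3.3, SAP 8.8 and SAP 11.2, name the time point as the next Scheduled Clinic Visit after booster, in place of a month label.
- Report the actual days from booster to that sample (median and range) by arm.
- In SAP 13.3 and Table 4, state SAE follow-up by its visit definition and report its actual duration.
- Have the sponsor reconcile the booster-timing passages (Table 2b header and footnote a, the Synopsis and Protocol 5.2 text, SAP Table 3 header and footnote a) before any nominal month range is stated. Which timing applies is for the sponsor to settle.

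The cost is wording plus one descriptive row. Protocol 3.1 already requires booster and blood-draw times to be recorded, so no new data are needed and no model or analysis set changes.

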1.0 BACKGROUND AND RATIONALE

1.1 Background (Amended 25 February 2019)

Rabies is a disease caused by the rabies virus (family Rhabdoviridae, genus *Lyssavirus*), which is shed in the saliva of infected and symptomatic animals. The transfer via a bite from an infected animal is the most efficient route of transmission. Upon transmission and after a variable incubation period, it migrates to the central nervous system and leads to an acute, progressive encephalomyelitis that is nearly always fatal. The incubation period in humans is usually several weeks to months, but ranges from <1 week to >1 year (*World Health Organization* /WHO/ 2013). Without intensive care, death occurs within 2 weeks after the appearance of clinical symptoms (WHO 2013).

Rabies occurs in more than 150 countries and territories, indicating its worldwide presence. More than 60,000 people die of rabies every year and 95% of these deaths occur in Asia and Africa (WHO 2013). Rabies has in fact the highest case fatality ratio of any currently recognized infectious disease, being almost always fatal (WHO 2013).

Pre-exposure (PrEP) or post exposure prophylaxis (PEP) as per the recommend regimens are the only means of protection against rabies virus infection.

Pre-exposure prophylaxis is recommended for anyone who is at continual, frequent or increased risk for exposure to the rabies virus, as a result of *her/his* residence or occupation, including travelers in high-risk areas (WHO 2013).

Post-exposure prophylaxis: after suspected or proven exposure to rabies virus, prompt use of modern cell culture or embryonated egg-based rabies vaccines (CCEEVs) with proper wound management and simultaneous administration of rabies immunoglobulin (depending on the category of exposure) is almost invariably effective in preventing rabies, even after severe exposure (WHO 2013).

Protection against rabies is dependent on the presence of *Rabies Virus Neutralizing Antibodies* (RVNA). WHO recommended method to measure RVNA serum concentrations is Rapid Fluorescent Focus Inhibition Test (RFFIT). A neutralizing antibody titer of ≥ 0.5 IU/mL is regarded by the WHO as being an 'adequate' antibody response following rabies vaccination, and is used as a threshold in clinical trials.

Rabipur® is a **Purified Chick-Embryo Cell Culture** (PCEC) rabies vaccine indicated for active immunization against rabies in individuals of all ages. This includes pre-exposure prophylaxis (i.e. before possible risk of exposure to rabies), in both primary series and booster dose, and post exposure prophylaxis (i.e. after suspected or proven exposure to rabies).

The target subjects for this study have already received a primary series of PrEP with Rabipur® either following a conventional (days 1, 8 and 29) regimen alone or in combination with JE vaccination or following an accelerated (days 1, 4 and 8) regimen in combination with JE vaccination in the parent study V49_23.

Although in clinical trials persistence of adequate antibody concentrations for 2 years after immunization with Rabipur® without additional booster has been observed in 100% of subjects, and experience shows that Rabipur® booster doses are generally required every 2-5 years following the conventional PrEP regimen, as recommended by WHO and following current Rabipur® **Summary of Product Characteristics (SmPC)**, the requirement for and the timing of booster vaccination following an accelerated pre-exposure prophylaxis regimen have never been evaluated previously and will be characterized in this study.

